### **6.3.4 Use in Nursing Women**

It is unknown whether MK-7162 or pembrolizumab is excreted in human milk. Since many drugs are excreted in human milk, and because of the potential for serious adverse reactions in the nursing infant, participants who are breastfeeding are not eligible for enrollment.

## **6.4 Screen Failures**

Screen failures are defined as participants who consent to participate in the clinical study but are not subsequently enrolled in the study. A minimal set of screen failure information is required to ensure transparent reporting of screen failure participants to meet the Consolidated Standards of Reporting Trials (CONSORT) publishing requirements and to respond to queries from regulatory authorities. Minimal information includes demography, screen failure details, eligibility criteria, and any adverse events or serious adverse events (SAE) meeting reporting requirements as outlined in the entry guidelines.

## **6.5 Participant Replacement Strategy**

In order to adequately evaluate the safety of the doses administered in Part A (Dose Escalation and Confirmation Phase), all participants enrolled must meet the criteria for evaluability for the first 2 cycles (42 days from the first dose of study medication). Criteria for evaluability of participants in Part B (Dose Expansion Phase) will be clarified in a future protocol amendment.

Participants are considered non-evaluable and will be replaced if:

- They are allocated but not treated
- They discontinue from the trial prior to completing all the safety evaluations for reasons other than treatment-related AEs
- They receive less than 90% of the total oral MK-7162 or pembrolizumab infusion in Cycle 1 and Cycle 2 and did not experience a DLT.

Participants who are not evaluable will be replaced unless accrual to the cohort has stopped. Non-evaluable participants will not be counted toward the total number of participants in the cohort for DLT evaluation.

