An mTPI design [Ji, Y. and Wang, S.-J. 2013] will be used to identify and confirm the RP2D of MK-7162 in combination with pembrolizumab. Participants will initially be enrolled in the first dose-level cohort, receiving MK-7162 monotherapy for Cycle 1, and then receiving MK-7162 in combination with pembrolizumab for subsequent cycles (Cycles 2 to Cycle 36). Lower and/or higher doses of MK-7162 may then be explored depending on the combined safety, PK, PD, and preliminary efficacy data available at each dose level. The dose of pembrolizumab will remain constant at 200 mg IV Q3W.

The final number of participants enrolled will depend on the DLT observations and what dose is ultimately identified as the RP2D using the mTPI design. For the purposes of dose escalation decisions from a safety perspective, participants will be considered evaluable for DLT if they have completed the 6-week DLT evaluation period (completed the first and second cycles or discontinued treatment due to a DLT).

Dose finding and confirmation in Part A of the trial will end after 14 participants have been treated at any of the selected doses (which may include optional doses). In the event the dose-finding decision is not to stay at the current dose based on the 14 participants, the dose may be escalated or de-escalated and additional participants may be treated. The pool-adjacent-violators algorithm [Ji, Y. and Wang, S.-J. 2013] will be used to estimate the DLT rates under the assumption of monotonicity between DLT rates and dose levels. The dose with an estimated DLT rate closest to 30% may be treated as a preliminary RP2D. The totality of the data will be considered before deciding on the dose(s) to carry forward to Part B (dose expansion).

The primary objective is to identify the RP2D of MK-7162 for use in combination with pembrolizumab. The preliminary RP2D may be the same as the MTD/MAD, or the preliminary RP2D may be selected based on overall exposure, emerging safety and tolerability data, PK data, PD data, and preliminary clinical benefit data from this study.

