
A D or DU decision at the lowest dose level will stop the trial. An E decision at the highest dose level will result in staying at that level. During dose finding, it may be acceptable to de-escalate to an intermediate dose that was not predefined and not previously studied if evaluation of toxicity at such a dose is desired. If this approach is taken, 3 to 6 new participants may be enrolled at the new intermediate dose, and the aforementioned rules should be used to determine further enrollment at this dose level.

Dose finding will end after 14 participants have been enrolled at any of the tested doses (including intermediate doses). In the event the dose-finding decision is not to stay at the current dose based on the 14 participants, the dose may be escalated or de-escalated and additional participants may be treated.

The pool-adjacent-violators-algorithm [Ji, Y. and Wang, S.-J. 2013] will be used to estimate the DLT rates across doses. The dose with an estimated DLT rate closest to 30% will be treated as a preliminary MTD. The final RP2D for future studies will be based on all available safety and tolerability assessments from the Dose Escalation and Confirmation Phase, Dose Expansion Phase, as well as PK and PD data, and preliminary efficacy assessments from this trial.

Note that although 30% was the target toxicity rate used to generate the guidelines in [\[Table 1\]](#), the observed rates of participants with DLTs at the MTD may be slightly above or below 30%.

Table 1 Dose-finding Rules per mTPI Design

Number of participants with at least 1 DLT	Number of Participants Evaluable for DLT at Current Dose											
	3	4	5	6	7	8	9	10	11	12	13	14
0	E	E	E	E	E	E	E	E	E	E	E	E
1	S	S	S	E	E	E	E	E	E	E	E	E
2	D	S	S	S	S	S	S	E	E	E	E	E
3	DU	DU	D	S	S	S	S	S	S	S	S	S
4		DU	DU	DU	D	D	S	S	S	S	S	S
5			DU	DU	DU	DU	DU	D	S	S	S	S
6				DU	DU	DU	DU	DU	D	S	S	S
7					DU	D						
8						DU						
9							DU	DU	DU	DU	DU	DU
10								DU	DU	DU	DU	DU
11									DU	DU	DU	DU
12										DU	DU	DU
13											DU	DU
14												DU

DLT = Dose limiting toxicity; D = De-escalate to the next lower dose; DU = The current dose is unacceptably toxic; E = Escalate to the next higher dose; S = Stay at the current dose.

Target toxicity rate = 30%

Flat noninformative prior Beta (1,1) is used as a prior and  $\epsilon_1=\epsilon_2=0.03$  [Ji Y, Li Y, Bekele BN 2007], [Ji, Y., et al 2007], [Ji, Y. and Wang, S.-J. 2013]

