
 
Any Grade 3 or 4 nonhematological toxicity (not including laboratory, unless clinically significant medical intervention is required to treat the participant, or the abnormality leads to hospitalization, or the abnormality persists for >1 week)
 
	Yes	Treatment may be restarted when AE resolves back to baseline or to Grade 1	Decrease dose by 1 dose level	If AE persists for 12 weeks without resolution following reduction in dose Permanent discontinuation from study treatment should be considered for any severe or life-threatening event

If toxicity is attributed to MK-7162, and requires a treatment hold and does not resolve to Grade 0-1 within 12 weeks after the last treatment, then MK-7162 should be discontinued.

With Investigator and Sponsor agreement, participants with a laboratory adverse event still at Grade 2 after 12 weeks may continue treatment in the trial only if asymptomatic and controlled.

After any Grade 4, drug-related adverse event, participants should not restart study treatment without consultation with the Sponsor (Toxicity must have resolved to Grade 0-1 or baseline prior to restarting).

Pembrolizumab treatment will be modified for the adverse events described Section 7.2.4.2.

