## **8. Discontinuation/Withdrawal Criteria**

### **8.1 Discontinuation of Study Treatment**

Discontinuation of study treatment does not represent withdrawal from the study.

As certain data on clinical events beyond study treatment discontinuation may be important to the study, they must be collected through the participant's last scheduled follow-up, even if the participant has discontinued study treatment. Therefore, all participants who discontinue study treatment prior to completion of the protocol-specified treatment period will still continue to participate in the study as specified in Section 2 - SoA and Section 9.11.3 – Discontinued Participants Continuing to be Monitored in the Study.

Participants may discontinue study treatment at any time for any reason or be dropped from the study treatment at the discretion of the investigator should any untoward effect occur. In addition, a participant may be discontinued from study treatment by the investigator or the Sponsor if study treatment is inappropriate, the trial plan is violated, or for administrative and/or other safety reasons. Specific details regarding procedures to be performed at study treatment discontinuation are provided in Section 9.1.9 – Withdrawal/Discontinuation.

A participant must be discontinued from study treatment but continue to be monitored in the study for any of the following reasons:

- The participant or participant's legally acceptable representative requests to discontinue study treatment.
- The participant interrupts study medication administration for more than 12 consecutive weeks.
- The participant interrupts MK-7162 for more than 84 (QD) cumulative missed doses.
- The participant has a medical condition or personal circumstance which, in the opinion of the investigator and/or sponsor, places the participant at unnecessary risk from continued administration of study treatment.
- The participant has a confirmed positive serum or urine pregnancy test.
- Non-compliance with trial treatment or procedure requirements.
- Confirmed radiographic disease progression outlined in Section 9.11 – Visit Requirements (Exception is if Sponsor approves treatment continuation).
- Unacceptable adverse experiences as described in Section 9.3 – Adverse Events, Serious Adverse Events and Other Reportable Safety Events.
- Intercurrent illness other than another malignancy as noted above (Section 5.1.1 – Dose Escalation and Confirmation) that prevents further treatment administration.

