## 10.5 Analysis Populations

### 10.5.1 Safety Analysis Populations

The ASaT population will be used for the analysis of safety data in this study. The ASaT population consists of all participants who received at least one dose of study treatment. In case of treatment administration errors, participants will be analyzed according to the treatment they actually received. The DLT evaluable population includes ASaT participants that were observed for safety for 42 days after the first dose of assigned treatment or experienced a DLT prior to 42 days after the first dose of assigned treatment. The replacement participants will also be considered evaluable if the above specified criteria are met. See Section 6.5 for details.

At least one laboratory or vital sign measurement obtained subsequent to at least one dose of study treatment is required for inclusion in the analysis of each specific parameter. To assess change from baseline, a baseline measurement is also required.

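### Sections 5.1.1 and 6.5, which govern cohort decisions, can leave out a participant with an observed in-window DLT whom the SAP (10.5.1) counts as DLT-evaluable

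*Combined protocol and SAP*

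**What the plan says.** Three sections say who is evaluable for DLT.

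- **5.1.1**, for dose-escalation decisions: the participant has "completed the first and second cycles or discontinued treatment due to a DLT".
- **6.5**, for replacement: a participant is non-evaluable if never treated, or if "They discontinue from the trial prior to completing all the safety evaluations for reasons other than treatment-related AEs", or on receiving "less than 90% of the total oral MK-7162 or pembrolizumab infusion in Cycle 1 and Cycle 2 and did not experience a DLT". The consequence is that "Non-evaluable participants will not be counted toward the total number of participants in the cohort for DLT evaluation".
- **10.5.1**, the SAP population: treated participants "observed for safety for 42 days after the first dose of assigned treatment or experienced a DLT prior to 42 days" after first dose. It then refers to 6.5 for details.

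Table 1 in 5.5.3.1 is indexed by "Number of Participants Evaluable for DLT at Current Dose". Under 7.2.2 a related Grade 3 or higher nonhematologic event is in general a DLT. For Grade 3 or 4 nonhematological toxicity, Table 4 holds MK-7162 and then says: "Treatment may be restarted when AE resolves back to baseline or to Grade 1". A DLT therefore need not end treatment.

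On leaving the trial, 8.1 states: "Discontinuation of study treatment does not represent withdrawal from the study". The treatment-duration paragraph of 5.1.1 instead lists reasons for stopping treatment, including progression and intercurrent illness, and says that participants are then discontinued from the study. Later paragraphs of 5.1.1 nevertheless describe follow-up after treatment stops.

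**The concern.** In 6.5 the DLT exception is attached to the under-dosing item only. The early-exit item looks solely at why the participant left, not at what was observed first. Someone who has already shown a DLT has given the information that the design needs; nothing that happens later can undo it. Removing that person discards an event and, after replacement, gives the slot to a participant who may be DLT-free. The error runs one way: the apparent DLT rate falls and the Table 1 decision can become less cautious, in cohorts that may hold only three participants. DLT incidence is the primary safety endpoint (10.4.2), and the cohort count would then differ from the SAP's own DLT-evaluable population.

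**Working it through.** **Step 1: two participants, three definitions.**

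| Participant with a DLT in the window that did not end treatment | 5.1.1 | 6.5 | 10.5.1 |
|---|---|---|---|
| A. Leaves the trial before Day 42 for a reason other than a treatment-related AE | Not evaluable | Not evaluable, replaced | Evaluable |
| B. Stops treatment before completing Cycle 2 for another reason, but stays in the trial | Not evaluable | Evaluable | Evaluable |

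For A, 5.1.1 and 6.5 agree and 10.5.1 differs. For B, 5.1.1 stands alone: the early-exit item of 6.5 needs exit from the trial, and its under-dosing item exempts anyone with a DLT. Whether a participant who stops for progression is A or B depends on whether the treatment-duration paragraph of 5.1.1 or 8.1 is followed. The reference from 10.5.1 to 6.5 does not settle A, because 6.5 gives the opposite answer.

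**Step 2: reproduce the Table 1 cells.** Inputs from Table 1: target 0.30, both epsilons 0.03, prior Beta(1,1). With x DLTs in n participants the posterior is Beta(1+x, 1+n−x). Each decision is scored by posterior probability divided by interval length: E on (0, 0.27), S on (0.27, 0.33), D on (0.33, 1). The largest score wins.

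| x/n | E | S | D | Result | Printed | P(rate > 0.33) |
|---|---|---|---|---|---|---|
| 0/3 | 2.65 | 1.37 | 0.30 | E | E | 0.20 |
| 1/3 | 1.10 | 1.76 | 0.89 | S | S | 0.60 |
| 1/4 | 1.52 | 2.05 | 0.70 | S | S | 0.47 |
| 1/6 | 2.24 | 2.12 | 0.40 | E | E | 0.27 |
| 2/7 | 1.38 | 2.53 | 0.71 | S | S | 0.48 |

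For 0/3, for example, E = (1 − 0.73⁴)/0.27 = 0.716/0.27 = 2.65.

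**Step 3: count the same participants both ways.** Participant A has a DLT, is dropped, and is replaced by someone without a DLT. The 6.5 set gives (x−1)/n; the 10.5.1 set gives x/(n+1).

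- 0/3 = E against 1/4 = S. If 10.5.1 governed and no replacement were enrolled, the count would be 1/3, also S.
- 1/6 = E against 2/7 = S.
- No change in some cells: 0/5 = E against 1/6 = E.
- If the replacement also has a DLT: 1/3 = S against 2/4 = S, no change.

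The replacement is DLT-free with probability 80%, 70% or 60% if the true rate is 20%, 30% or 40% (assumed range).

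Over the legible part of the printed table (up to six DLTs), 17 of 63 such pairs differ, each with the less cautious entry on the 6.5 side. One of the 17 uses the printed 2/10 = E, which recomputes as S. Printed 6/11 and 6/12 also differ from a recomputation (6/11 under an assumed 0.95 exclusion cut-off), though none of the 17 uses them. The two examples above rest on none of these cells.

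**Step 4: effect on the final estimate.** Section 10.6.2 uses an 80% credible interval with a Beta(1,1) prior. Without the participant: 3/14 = 21%, Beta(4,12), 12% to 39%. With the participant: 4/15 = 27%, Beta(5,12), 16% to 44%. The intervals overlap heavily.

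**The case against.** The trigger is narrow. Treatment-related toxicity that makes a participant stop treatment in Cycle 1 or 2 is itself a DLT (7.2.2, criterion 6) and is kept by 5.1.1. Withdrawal because of the toxicity arguably falls outside the early-exit item of 6.5. What is left is a DLT followed by an unrelated exit. There are safeguards too: the trial is open-label, 5.1.1 bases dose exploration on the combined data at each level, 5.5.3.1 says that at 0/3 the dose can escalate, and the DLT stays in the ASaT data and the DLT listing (10.6.2). All of this stands and limits the size of the point. It does not remove it, because the written counting rule still tells the team to leave the event out, and the exception in the neighbouring item suggests an oversight.

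A reader might infer more than the documents support:

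- **That all three sections conflict with one another over the participant who withdraws.** They do not: 5.1.1 and 6.5 both exclude, and only 10.5.1 includes.
- **That withdrawal of consent is the only trigger.** The treatment-duration paragraph of 5.1.1, if followed, widens it; participant B needs no exit at all.
- **That 10.5.1 ignores the 90% dosing requirement.** Its reference to 6.5 can be read as bringing that in. This, and naming the analysis set in 10.6.2, are clarifications.
- **That DLT criterion 7 (a Cycle 3 delay of more than 2 weeks) shows the same fault.** The window can be read as applying to when the toxicity occurs. That is a separate ambiguity, to be reconciled on its own.

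**Conclusion.** The point holds as a definitional mismatch that can bias a cohort decision towards less caution. It should be fixed, but it is not a threat to the trial's conclusions. Its size is one Table 1 step in the affected cells, such as escalate instead of stay at 0/3 against 1/4. P(rate > 0.33) is 20% on one count and 47% on the other. The final DLT estimate changes little.

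This rests on three assumptions: 6.5 is applied as written; a participant outside the Table 1 denominator is also outside its numerator; and the replacement is DLT-free. The documents give no frequency for the case and none is assumed here; it is likely to be uncommon. It would be wrong to conclude that a DLT is hidden or that escalation would be forced.

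**What to change.** 1. In 6.5, give the early-exit item the DLT exception that the under-dosing item already carries.
2. In 5.1.1, align the evaluability wording with 10.5.1, so that a participant with an observed DLT in the window is always counted, whatever happens afterwards.
3. State that this one set is used for Table 1, the pool-adjacent-violators estimate and the 80% credible interval in 10.6.2. In the same edit, say in 10.5.1 whether the 90% dosing requirement of 6.5 applies.
4. Reconcile the treatment-duration paragraph of 5.1.1 with 8.1 on whether stopping treatment means leaving the study.

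The cost is a few words in 5.1.1, 6.5, 8.1, 10.5.1 and 10.6.2. No participants or procedures are added, and no dose or clinical management rule is proposed.

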#### **5.1.1 Dose Escalation and Confirmation**

This study will evaluate the safety and tolerability of MK-7162 alone and the safety, tolerability, and preliminary efficacy of MK-7162 in combination therapy with pembrolizumab.

All participants will be required to undergo a newly performed tumor biopsy during Screening, unless deemed medically unsafe by the Investigator. An additional on-study biopsy at one of two timepoints will also be required, unless deemed medically unsafe by the Investigator, with the biopsy at the other time point being optional. Initially, this biopsy will be required to occur on Cycle 2 Day 1 predose (prior to administration of MK-7162 study medication and prior to administration of IV pembrolizumab on that day), with a Cycle 3 Day 15 biopsy being optional. This will allow full characterization of the MK-7162 dose and intratumoral PD response relationship after three weeks of MK-7162 monotherapy. In addition, this tissue biopsy will facilitate characterization of the MK-7162 dose that maximally inhibits intratumoral IDO1. After a sufficient number of biopsy specimens at the Cycle 2 Day 1 timepoint have been collected, the Sponsor may notify the sites that the Cycle 2 Day 1 biopsy will become optional and the Cycle 3 Day 15 biopsy will be required. Characterization of the MK-7162 dose and intratumoral PD response relationship at this time point will confirm whether the intratumoral PD effect of a given MK-7162 dose is maintained during concurrent PD-1 blockade with pembrolizumab, since IDO1 upregulation occurs during immune responses.

Treatment allocation will be accomplished by nonrandom assignment through the interactive voice response system/integrated web response system IVRS/IWRS. Participants will receive MK-7162 monotherapy during the first treatment cycle followed by MK-7162 in combination with pembrolizumab for subsequent cycles.

MK-7162 will be administered PO QD, every day of each 21-day (3-week) cycle. Starting on Cycle 2, Day 1, MK-7162 will be administered in combination with pembrolizumab 200 mg IV, which will be administered on Day 1 of every cycle (every 3 weeks). The DLT evaluation period will be 2 cycles (6 weeks). Treatment of the first and second participants

enrolled in each cohort will occur at least 7 days apart. Treatment of the second and third participants enrolled in each cohort will occur at least 3 days apart.

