8. Missing >25% of MK-7162 doses as a result of drug-related AE(s) during the first 2 cycles of treatment
9. Grade 5 toxicity

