**Table 4 MK-7162 Dose Modification and Treatment Discontinuation Guidelines for Drug-Related Adverse Events**

Toxicity	Hold Treatment	Criteria for Restarting Treatment	Dose/Schedule for Restarting Treatment	Criteria for Discontinuation after Consultation with Sponsor
Hematological toxicities:				
• Any Grade 1 hematological toxicity	No	N/A	N/A	N/A
• Any Grade 2 hematological toxicity, or Grade 3 toxicity that persists for ≤5 days	Per medical assessment of the investigator	If treatment held, may be restarted when AE resolves back to baseline or to Grade 1	Per medical assessment of the Investigator: may decrease dose by 1 dose level	If AE persists for 12 weeks without resolution following reduction in dose
• Any Grade 3 hematologic toxicity that persists for >5 days, or Grade 4 hematological toxicity • Febrile neutropenia • Grade 3 thrombocytopenia of any duration if associated with bleeding	Yes	Treatment may be restarted when AE resolves back to baseline or to Grade 1	Decrease dose by 1 dose level	If AE persists for 12 weeks without resolution following reduction in dosing schedule  Permanent discontinuation should be considered for any severe or life-threatening event
Nonhematological toxicities:				
Toxicity	Hold Treatment	Criteria for Restarting Treatment	Dose/Schedule for Restarting Treatment	Criteria for Discontinuation after Consultation with Sponsor
• Any Grade 1 nonhematological toxicity • Grade 2 alopecia • Grade 2 fatigue	No	N/A	N/A	N/A
• Any Grade 2 nonhematological toxicity except Grade 2 alopecia and Grade 2 fatigue	Per medical assessment of the investigator	If treatment held, may be restarted when AE resolves back to baseline or to Grade 1	Per medical assessment of the Investigator: may decrease dose by 1 dose level	If AE persists for 12 weeks without resolution following reduction in dose

Toxicity	Hold Treatment	Criteria for Restarting Treatment	Dose/Schedule for Restarting Treatment	Criteria for Discontinuation after Consultation with Sponsor

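### Missing 5 to 10 of 42 MK-7162 doses through drug toxicity has no single DLT status: uncounted under 6.5, not a DLT under 7.2.2 item 8, evaluable under 5.1.1

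*Combined protocol and SAP*

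**What the plan says.** **Replacement (Section 6.5).** The third criterion for being non-evaluable is "They receive less than 90% of the total oral MK-7162 or pembrolizumab infusion in Cycle 1 and Cycle 2 and did not experience a DLT". Such participants are replaced unless the cohort has stopped accruing and, replaced or not, they do not count towards cohort size for DLT evaluation. The second criterion, on leaving the trial early, applies only to exits "for reasons other than treatment-related AEs". The third has no limit by cause.

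**DLT definition (Section 7.2.2).** Item 8 is "Missing >25% of MK-7162 doses as a result of drug-related AE(s) during the first 2 cycles of treatment". Item 2 counts Grade 4 hematologic toxicity only when it lasts 7 days or more, with separate rules for thrombocytopenia.

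**Dose holds (Section 7.2.4.1, Table 4).** MK-7162 must be held, until baseline or Grade 1, for "Any Grade 3 hematologic toxicity that persists for >5 days, or Grade 4 hematological toxicity". For Grade 2 toxicities other than alopecia and fatigue, the hold is left to the investigator.

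**Other evaluability definitions.** Section 5.1.1 counts participants who complete the first two cycles or stop treatment because of a DLT; it sets no dose condition and does not refer to 6.5. Section 10.5.1 takes treated participants who were "observed for safety for 42 days after the first dose of assigned treatment" or had a DLT before then, and closes with a reference to 6.5.

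**Use.** Table 1 acts on the number evaluable and the number with a DLT. Section 10.6.2 uses the DLT data for the pooled-adjacent-violators estimate and an 80% credible interval.

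**The concern.** Two limits apply to the same dosing in the same window, and they do not meet. Between them lies a range of missed doses that is too many to be evaluable under 6.5 and too few to be a DLT under item 8. When the doses were missed because of the drug, the participant's status in the primary safety endpoint depends on which section is applied.

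The plan handles the neighbouring case with care: someone who leaves the trial because of a treatment-related AE is not replaced under the second criterion. Someone who stays but has doses held for a treatment-related AE gets no such distinction under the third.

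Cohorts are as small as 3, so the status of one person can decide whether the dose goes up, stays, comes down or is excluded.

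**Working it through.** **1. Scheduled doses.** Section 5.1.1: "MK-7162 will be administered PO QD, every day of each 21-day (3-week) cycle". The DLT window is two cycles, so 2 × 21 = 42 doses, which agrees with the 42 days given in 6.5 and 10.5.1.

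**2. The two limits** (m = doses missed).
- 6.5: (42 − m)/42 < 0.90. At m = 4, 38/42 = 90.48%, evaluable. At m = 5, 37/42 = 88.10%, non-evaluable.
- 7.2.2 item 8: m/42 > 0.25. At m = 10, 10/42 = 23.81%, not a DLT. At m = 11, 11/42 = 26.19%, a DLT if drug-related.

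The range between them is m = 5 to 10. Visit windows move it slightly: with 39 scheduled doses it is 4 to 9, with 45 it is 5 to 11. This counts whole missed doses. If the 90% is read as milligrams, a toxicity-driven dose reduction could also fall below it.

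**3. Can the case arise without another DLT item being met?** Yes. Table 4 requires a hold for Grade 3 hematologic toxicity beyond 5 days and for Grade 4 hematologic toxicity. Item 2 does not score the former (bleeding thrombocytopenia aside), nor Grade 4 lasting under 7 days (thrombocytopenia aside). Discretionary Grade 2 holds are not DLTs by grade either.

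**4. Effect on Table 1.** One such participant in the cohort. The middle column applies before a replacement has been observed, or if accrual has stopped. The last column is not the present rule; it shows what the choice of status decides.

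| Treated, other DLTs | Counted as non-DLT (5.1.1) | Left out (6.5) | If scored as a DLT |
|---|---|---|---|
| 6 treated, 1 DLT | 1/6 = E | 1/5 = S | 2/6 = S |
| 4 treated, 2 DLTs | 2/4 = S | 2/3 = D | 3/4 = DU |
| 5 treated, 3 DLTs | 3/5 = D | 3/4 = DU | 4/5 = DU |
| 3 treated, 0 DLTs | 0/3 = E | 0/2, below the minimum of 3 | 1/3 = S |

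Not every cohort is affected: 0/6 and 0/5 are both E.

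**5. Effect on the estimated rate.** Let p be the share with a DLT and q the share in the range. The expected rate is p/(1 − q) if they are left out and replaced, p if counted as non-DLTs, and p + q if scored as DLTs. Neither p nor q is in the documents. Assuming p = 0.30 and q = 0.10:
- left out: 0.30/0.90 = 0.333; chance of 0 DLTs in 3 = (1 − 0.333)³ = 0.296
- non-DLT: 0.300; 0.70³ = 0.343
- DLT: 0.400; 0.60³ = 0.216

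Over p = 0.20 or 0.30 and q = 0.05 to 0.20, the three rates span 0.211 to 0.375, 0.200 to 0.300, and 0.250 to 0.500.

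A single-dose illustration: with 14 treated, 4 DLTs and one such participant, the crude rate is 4/14 = 28.6%, 4/13 = 30.8% or 5/14 = 35.7%. Table 1 says S in all three, but the estimate moves around the 30% target.

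**The case against.** The limits answer different questions. The 90% limit asks whether exposure was enough to call someone DLT-free; the 25% limit asks whether missed dosing is itself dose-limiting. They need not coincide, and declining to credit an under-exposed participant as DLT-free is defensible. Many serious causes of a hold are already DLTs under other items: most nonhematologic Grade 3 or higher AEs, febrile neutropenia, treatment-related discontinuation, delays beyond 2 weeks. The AEs are not lost either. These participants stay in the ASaT population, AEs are summarised by dose level, and dose selection draws on all the data. All of this stands, and it narrows the point. It does not settle which definition feeds Table 1, because 5.1.1 and 6.5 still give different counts.

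Three stronger readings are tempting, and the documents do not support them.
- A reader might infer that replacement makes a dose look safer than it is. The criterion removes only participants without a DLT, so it raises the observed DLT rate relative to counting them as non-DLTs. It understates toxicity only against a rule that scored them as DLTs, which 7.2.2 does not do. For the same reason p + q is not a DLT rate under the present text.
- A reader might infer that 10.5.1 flatly contradicts 6.5, so that dose decisions and final analysis certainly use different people. Because 10.5.1 refers to 6.5, it can be read as adopting the 90% condition. The clean conflict is with 5.1.1.
- A reader might infer that carrying the second criterion's limit over to the third would be enough. Alone, that would enter these participants as non-DLTs and loosen escalation: 1/5 (S) becomes 1/6 (E). With assumed p = 0.20 and q = 0.10 to 0.20, the chance of 0/3 would rise from 0.471 to 0.422 (p/(1 − q) = 0.222 to 0.250) to 0.80³ = 0.512.

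**Conclusion.** The concern holds as a conflict between definitions that feed a decision rule. With 42 scheduled doses, 5 to 10 missed for drug-related AEs, and no other DLT item met, a participant is uncounted under 6.5, not a DLT under 7.2.2 item 8, and evaluable under 5.1.1 and on the wording of 10.5.1. The range is exact on the documents' own figures, apart from small shifts with visit windows, and Table 4 holds can produce it. One such participant can change the Table 1 action in small cohorts and also moves the final DLT-rate estimate.

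No overall direction of bias can be claimed, since it depends on what exclusion is compared with. Frequency is unknown, so the rates calculated from p and q are illustrations only.

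**What to change.** Reconcile Sections 5.1.1, 6.5, 7.2.2 item 8 and 10.5.1 so that one evaluability definition governs both the mTPI decisions and the final DLT-rate analysis, and each toxicity-driven dose shortfall has one stated status. Which status is for the sponsor to choose. The text should also say whether the 90% is counted in doses or milligrams.

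At each dose decision, tabulate by dose level the participants with toxicity-driven missed doses, including any who were replaced, next to the DLT count. At the final analysis, show the DLT rate with these participants excluded, counted as non-DLTs and counted as DLTs. If dose finding is already over, this last step and a statement of the rule actually applied are what remain to be done.

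The cost is wording in four sections, one more line in the dose-decision table and two further rate estimates. The tolerability picture at a dose may look less favourable once these participants are shown.
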